9.2. Other Safety Analyses

9.2.1. Overview of Planned Other Safety Analyses

The other safety analyses will be based on the Safety population, unless otherwise specified.

Table 10 provides an overview of the planned other safety analyses, with further details of data displays being presented in Section 11.15.

Table 10 Overview of Planned Other Safety Analyses

Endpoints	Absolute				Change from Baseline			
	Summary		Individual		Summary		Individual	
	T	F	F	L	T	F	F	L
CV								
Investigator-Reported Reason for Death	Y [1]				Y[1]			
Disclosure Requirements								
CTR								
SAEs by PT (descending frequency): Overall, fatal, drug-related, drug-related fatal [2]	Y (x4)							
Most Frequent 10 AEs [3]	Y							
FDAAA / EMA								
SAEs [4]	Y							
Common ($\geq 5\%$) Non-serious AEs [5]	Y							
Other								
Aspartate aminotransferase (AST), alanine aminotransferase (ALT), alkaline phosphatase, bilirubin, creatinine, gamma glutamyl transferase (GGT)[6]	Y (x2) [7]	Y [8]	Y (x2) [9]	Y[10]	Y (x2)	Y [8]		
Creatinine [11]				Y	Y (x2) [12]			
Pregnancies				Y				
Requirement for Mexican MoH [13]				Y (x3)				
Other CV events: Arrhythmias [14],	Y (x2)[15]			Y (x6) [16]				

Endpoints	Absolute				Change from Baseline			
	Summary		Individual		Summary		Individual	
	T	F	F	L	T	F	F	L
Valvulopathy, Pulmonary Hypertension, Peripheral Arterial Thromboembolism, Deep Venous Thrombosis / Pulmonary Embolism, Revascularization (other than revascularizations intended for CEC adjudication)								
Subject Profiles				Y				
Creatinine Assay Issue Sensitivity Analyses								
Creatinine	Y				Y			
eGFR					Y (x2)			

NOTES :

- T = Table, F = Figure, L = Listing, Y = Yes display generated.
- Stats Analysis = Represents TFL related to any formal statistical analyses (i.e. modelling) conducted.
- Summary = Represents TFL related to any summaries (i.e. descriptive statistics) of the observed raw data.
- Individual = Represents FL related to any displays of individual subject observed raw data.

[1] ITT population.

[2] Frequency overall and by Preferred Term for the On-therapy time period; required for disclosure.

[3] Most frequent 10 AEs in each treatment group; required for disclosure.

[4] Frequency overall and by SOC and Preferred Term for the On-therapy time period (Subjects with SAEs, SAEs, Drug-related SAEs, Fatal SAEs, Drug-related Fatal SAEs); required format for disclosure.

[5] Frequency overall and by SOC and Preferred Term for the On-therapy time period; required for disclosure, to be indicated as collected via "Non-systematic Assessment".

[6] Creatinine will include baseline local and Central lab data and post-baseline scheduled visit Central lab data.

[7] Raw, potential clinical concern.

[8] Box and whisker plot for creatinine and change from baseline creatinine.

[9] Evaluation of drug-induced serious hepatotoxicity (EDISH) plot of ALT vs total bilirubin (ULN = Upper Limit of Normal), maximum vs baseline for ALT (ULN).

[10] Subjects with abnormalities of potential clinical concern.

[11] Creatinine will include baseline and post-baseline scheduled visit Central lab.

[12] Potential clinical concern for shifts from baseline and for change from baseline by baseline eGFR.

[13] MoH = Ministry of Health.

[14] Excluding atrial fibrillation/flutter which is an AESI.

[15] Frequency for On-therapy and Post-therapy combined, On-therapy time periods.

[16] Subject profiles for each of the "Other CV events".

GSK has identified other CV events of special interest for studies. Such events (arrhythmias [other than atrial fibrillation/flutter which is an AESI], valvulopathy, pulmonary hypertension, peripheral arterial thromboembolism, deep venous thrombosis / pulmonary embolism, revascularization [other than revascularizations intended for CEC

adjudication]) that meet SAE criteria or are non-serious events that result in discontinuation of investigational product will have additional event-specific details recorded in the eCRF. Frequency of the other CV events of special interest will be summarized, and subject profiles will be provided. These events will be identified as described in Section 11.6.3.

Summaries of creatinine will include baseline local and Central lab data and post-baseline scheduled visit Central lab data. Summaries of creatinine by visit will include the frequency of subjects with post-baseline creatinine values of 1.5 times baseline and 2 times baseline, stratified by baseline eGFR category (Normal ≥ 90 , Mild ≥ 60 to < 90 , Moderate ≥ 30 to < 60 , and Severe < 30 ml/min/1.73m²). Box plots of creatinine and change from baseline creatinine will be provided. In addition, as a sensitivity analysis, a summary of shifts from baseline with respect to potential clinical concern will be done including baseline and post-baseline scheduled visit Central lab data.

During the study a creatinine assay quality issue was reported by the central lab which resulted in artificially high values. In addition to creatinine results, eGFR values may have been affected. The central lab indicated that this issue was restricted to samples assayed between 01Oct2016 and 13Jan2017 for sites in a subset of countries. It is anticipated that approximately 5%-20% of creatinine results that were assayed during this time period may be artificially high. Summaries will be provided to allow the potential impact of this issue to be evaluated. In particular, four summaries will be rerun excluding all data with sample dates in the time frame 26Sep2016-13Jan2017 (inclusive) for sites in the following countries: Argentina, Canada, Mexico, Peru, US. The specified time frame represents the earliest and latest dates of affected samples based on data provided by the central lab. The four summaries will include those for potential clinical concern for creatinine and change from baseline creatinine, along with the two MMRM analyses for change from baseline eGFR.

The Requirement for the Mexican Ministry of Health will be composed of the following:

- Listing of non-serious AEs for subjects at Mexican sites (this is expected to only include non-serious AESIs and non-serious AEs leading to discontinuation of IP)
- Listing of clinical events and SAEs for subjects at Mexican sites
- Listing of SAEs for subjects at non-Mexican sites

Subject profile listings will be generated for the following subjects in the Safety population: subjects with AESIs, subjects with AEs leading to discontinuation of IP, subjects withdrawn from study, and subjects who died. The listings will include demography, disposition, medical/surgical procedures, medical history, medication, all reported AEs and SAEs, CV event, death, lab, and vital signs data.

Narratives will be generated for subjects in the Safety population experiencing SAEs, pregnancies, non-serious AEs leading to permanent discontinuation of IP, non-SAE deaths (if any), and the following non-serious AEs that did not lead to permanent discontinuation of IP, but which are of potential clinical importance: severe hypoglycaemic episodes (not meeting the definition of Serious as these are in the set of SAEs listed above), and hepatic events recorded on the Liver Events eCRF that met the

monitoring or stopping criteria. It is planned that some of these narratives will originate from the GSK ARGUS system; the remainder may be developed programmatically but would be provided separately from the other RAP-specified outputs by a group other than PPD.

Treatment details for relevant subjects will be provided electronically as a comma-separated values (CSV) file; this is intended for GSK Global Clinical Safety and Pharmacovigilance (GCSP) use and is not for inclusion with other listings.

Albiglutide pen injection failures and user errors are collected outside of the eCRF. Detailed information on reported cases at clinical sites that are related to the pen injector and the use of the pen injector and pen needle over the entire duration of the study are collected on specially designed forms that were completed by study subjects and study site staff. The information on these forms has been entered onto spreadsheets outside of the INFORM database. Summaries of these data, linked as appropriate to information on AEs, may be generated but would be provided separately from the other RAP-specified outputs by a group other than PPD.

9.3. Other Value Evidence and Outcomes Analyses

9.3.1. Overview of Planned Other Value Evidence and Outcomes Analyses

The other Value Evidence and Outcomes analyses will be based on the ITT population.

Table 11 provides an overview of the planned other efficacy analyses, with further details of data displays being presented in Section 11.15. As noted in Section 8.3.1, although not specified in the protocol, it was subsequently clarified in the Study Reference Manual and the eCRF Completion Guidelines that questionnaires were not to be completed after subjects discontinued study treatment; hence such data will be programmatically excluded from all summaries (but included in listings with corresponding flag).

Table 11 Overview of Planned Other Value Evidence and Outcomes Analyses

Endpoints	Absolute							Change from Baseline						
	Stats Analysis			Summary		Individual		Stats Analysis			Summary		Individual	
	T	F	L	T	F	F	L	T	F	L	T	F	F	L
In-patient Healthcare Resource Utilization				Y										
Study-specific Questionnaire				Y							Y (x2) [1]			

NOTES :

- T = Table, F = Figure, L = Listing, Y = Yes display generated.
- Stats Analysis = Represents TFL related to any formal statistical analyses (i.e. modelling) conducted.
- Summary = Represents TFL related to any summaries (i.e. descriptive statistics) of the observed raw data.
- Individual = Represents FL related to any displays of individual subject observed raw data.

[1] For Question 1 and Question 3.

In-patient healthcare resource utilization data (duration of stay) will be summarized overall and by level of care/ward.

Study-specific (Managing Diabetes) questionnaire data will be summarized categorically by question for the baseline and post-baseline assessments. For Question 1 and Question 3 the frequency of combinations of responses at baseline and post-baseline will be summarized. Summaries will exclude data assessed after subjects discontinue study treatment.

9.4. Electronic Health Record Ancillary Study

A separate RAP will be developed by Duke Clinical Research Institute (DCRI) for the Electronic Health Record Ancillary Study. Results from this exploratory investigation will be reported separately from and after the main clinical study report.

11. APPENDICES

Section	Appendix
RAP Section 4 : Analysis Populations	
Section 11.1	Appendix 1: Protocol Deviation Management and Definitions for Per Protocol Analysis
RAP Section 5 : Considerations for Data Analyses & Data Handling Conventions	
Section 11.2	Appendix 2: Time & Events
Section 11.3	Appendix 3: Assessment Windows
Section 11.4	Appendix 4: Treatment States and Phases
Section 11.5	Appendix 5: Data Display Standards & Handling Conventions 
 • Study Treatment & Sub-group Display Descriptors • Baseline Definitions & Derivations • Reporting Process & Standards
Section 11.6	Appendix 6: Derived and Transformed Data 
 • General • Study Population • Safety • Efficacy
Section 11.7	Appendix 7: Premature Withdrawals & Handling of Missing Data 
 • Premature Withdrawals • Handling of Missing Data
Section 11.8	Appendix 8: Values of Potential Clinical Importance
Section 11.9	Appendix 9: Multicenter Studies
Section 11.10	Appendix 10: Examination of Covariates and Subgroups
Section 11.11	Appendix 11: Multiple Comparisons & Multiplicity
Section 11.12	Appendix 12: Model Checking and Diagnostics for Statistical Analyses
Section 11.13	Appendix 13: Medication Groupings
Other RAP Appendices	
Section 11.14	Appendix 14: Abbreviations & Trade Marks
Section 11.15	Appendix 15: List of Data Displays

11.1. Appendix 1: Protocol Deviation Management and Definitions for Per Protocol Analysis

11.1.1. Important Protocol Deviations

Subject compliance to the protocol will be evaluated prior to unblinding the study (except for wrong study treatment administered, see Section 11.1.2) and subjects with important protocol deviations will be identified. Criteria for what constitutes an important protocol deviation are specified in the Protocol Deviation Management Plan (PDMP).

11.1.2. Exclusions from Per Protocol Analysis

The following criteria define the conditions which lead to exclusion of data from the PP analysis and are specified in the PDMP. These include protocol deviations which will be reviewed by a subgroup of the study team to assess and confirm whether they are likely to have sufficient impact to warrant the exclusion of subject data from the PP analysis. These reviews will occur before the database has been frozen for analysis. Assessment of whether a subject was dispensed the wrong study treatment (i.e. actual treatment differs from randomized treatment) will be confirmed after unblinding.

The PP analysis will be done using the Per-Protocol Analysis Time Period (see Section 11.6.4) and will include all randomized subjects who provide consent and receive at least one dose of study treatment, exclude data prior to treatment start date and data after the date of last dose of study treatment + 56 days, and exclude data via censoring for subjects experiencing the specified conditions.

Number	Data Exclusion Description	Data Excluded
01	Inclusion #1 – Did not have type 2 diabetes	Data on or after randomization (censored at day 1)
02	Exclusion #2 – Use of GLP-1 receptor agonist at Screening	Data on or after randomization (censored at day 1)
03	Non-study GLP-1 receptor agonist was taken	Data on or after first use of GLP-1 receptor agonist anytime after randomization
04	Incorrect study drug assignment of more than one container at a visit	Data on or after date that at least two containers with incorrect study drug are dispensed
05	Subject off study treatment for at least 56 consecutive days.	Data on or after the date off study treatment + 57 days

For criterion number 05, determination of whether subjects are off study treatment for at least 56 consecutive days will account for subjects who have gaps in study treatment as well as account for treatment stop date. For subjects with gaps who have multiple entries recorded in the Study Treatment Form eCRF, days off study treatment = (start date – previous stop date – 1). Exclude data on or after the earliest of the following:

- treatment stop date + 57 days
- IP stop date + 57 days, where IP stop date corresponds to the earliest such value for which days off study treatment is at least 56 days (if such cases of gaps in study treatment occurred).

For purposes of evaluating criterion 05 only, cases in which partial or missing stop dates are present will be handled as follows:

- Partial or missing last stop date will be imputed as specified for Treatment Stop Date in Section 11.6.1.
- Partial or missing stop dates other than last stop date will be handled as follows:
 - If imputing the earliest possible stop date consistent with the corresponding start date and subsequent start date results in days off study treatment < 56 days then do not exclude data. Otherwise handle as follows:
 - If only year is available, or if date is completely missing, then do not impute stop date and do not exclude data.
 - If month and year are available, but the day of month is missing, then determine the range of potential date values and use the middle of this range as the imputed stop date. The beginning of the potential range of date values is the maximum of the following two dates: start date + 1, the first of the month of the stop date of interest. The end of the potential range of date values is the last day of the month of the stop date of interest. If there is an even number of dates ($n=2m$) in the potential range of date values then use the date corresponding to the $(m+1)$ th of the ordered dates.

For purposes of evaluating criterion 05 only, cases in which partial or missing start dates are present will be handled as follows:

- Partial or missing start dates will be handled as follows:
 - If imputing the latest possible start date consistent with the corresponding stop date and previous stop date results in days off study treatment < 56 days then do not exclude data.
 - If imputing the earliest possible start date consistent with the corresponding stop date and previous stop date results in days off study treatment ≥ 56 days then exclude data based on the earliest possible start date.
 - Otherwise handle as follows:
 - If only year is available, or if date is completely missing, then do not impute start date and do not exclude data.
 - If month and year are available, but the day of month is missing, then determine the range of potential date values and use the middle of this range as the imputed start date. The beginning of the potential range of date values is the first of the month of the start date of interest. The end of the potential range of date values is the minimum of the following two dates: stop date - 1, the last day of the month of the start date of interest. If there is an even number of dates ($n=2m$) in the potential range of date values then use the date corresponding to the $(m+1)$ th of the ordered dates.

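### Per-Protocol criterion 05: a year-only stop date on a non-last dosing entry never triggers exclusion, even when every possible date gives a gap of at least 56 days

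*SAP*

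**What the plan says.** In SAP Section 11.1.2, criterion 05 reads "Subject off study treatment for at least 56 consecutive days", and what it removes is "Data on or after the date off study treatment + 57 days". The gap between two dosing entries is the later start date minus the previous stop date minus 1.

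The same section has special rules for partial or missing dates, used for this criterion only:

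- **Last stop date.** "Partial or missing last stop date will be imputed as specified for Treatment Stop Date in Section 11.6.1".
- **Any other stop date.** The only screening step is "If imputing the earliest possible stop date consistent with the corresponding start date and subsequent start date results in days off study treatment" below 56 days, in which case nothing is excluded. Otherwise a year-only or missing date meets this instruction: "If only year is available, or if date is completely missing, then do not impute stop date and do not exclude data". Where the record gives a month as well as a year, the programmer must "determine the range of potential date values and use the middle of this range as the imputed stop date".
- **Start date.** There are two screening steps. If the latest possible start gives under 56 days, nothing is excluded. Then: "If imputing the earliest possible start date consistent with the corresponding stop date and previous stop date results in days off study treatment" of 56 or more, data are excluded. Only cases left unresolved by both steps reach the year-only line.

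**The concern.** The earliest possible stop date gives the longest possible gap. Testing it alone can show that criterion 05 is certainly not met, but never that it certainly is. The start-date rule tests both extremes; the stop-date rule lacks the second test and sends every remaining year-only stop date to an instruction not to exclude. A gap that the record itself proves to be 56 days or longer is then ignored.

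This matters because criterion 05 is the only Per-Protocol condition that deals with interruptions of study treatment. The On-treatment and On-therapy periods run from first dose to last dose (plus 56 days for On-therapy), so by design they keep intermediate gaps. SAP Section 7.1.2 presents the Per-Protocol analysis as On-therapy plus the specified conditions. Table 5 lists it as a key sensitivity analysis, and its hazard ratio and non-inferiority p-value go on the forest plot.

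**Working it through.** The SAP gives no figure to reproduce here; the check is on the decision logic.

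**Inputs (SAP 11.1.2).** Gap = next start − previous stop − 1. Threshold: gap ≥ 56 days. Censoring begins at stop date + 57 days. The dates below are illustrative.

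**1. When is the gap certain?** For a stop recorded only as year Y, with the next start in a later year, the latest possible stop is 31 December of Y. The shortest gap is next start − 31 Dec − 1. Requiring at least 56 gives next start ≥ 31 Dec + 57 days. January has 31 days and 57 − 31 = 26, so the threshold is 26 February of Y+1. A restart on 25 February gives a shortest gap of 55 (uncertain); on 26 February it is 56 (certain). In a 365-day year, 365 − 56 = 309 restart dates fall in the certain zone. That is a calendar count, not a frequency of affected subjects.

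**2. Worked case.** Entry starts 10 Feb 2016, stop recorded as 2016 only, next entry starts 15 Jun 2017.

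- Longest gap (stop 11 Feb 2016): 490 − 1 = 489 days. This is not below 56, so the single screening step does not settle the case.
- Shortest gap (stop 31 Dec 2016): 166 − 1 = 165 days. Criterion 05 is met for every possible stop date.
- Decision as written: no imputation, no exclusion.
- Even with the latest possible stop, censoring should begin by 31 Dec 2016 + 57 days = 26 Feb 2017. The rule keeps at least 165 − 56 = 109 off-drug days (26 Feb to 14 Jun 2017) that criterion 05 would remove, plus the time after restart.

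**3. Same case with more date detail.** If the stop is recorded as December 2016, the middle of 1 to 31 December is 16 December. The gap is 181 − 1 = 180 days, and data are excluded from 16 Dec + 57 days = 11 Feb 2017. A midpoint gap is never shorter than the shortest possible gap, so month-and-year dates always catch a certain gap.

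**4. Mirror case for a start date.** Previous stop 5 Nov 2016, next start recorded as 2017 only. The earliest possible start is 1 Jan 2017, so the shortest gap is 57 − 1 = 56 days. The rule excludes, and 5 Nov 2016 + 57 days = 1 Jan 2017. A certain gap is acted on here and ignored in step 2.

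**5. Completely missing stop date.** The stop could fall on the day before the next start, so the shortest gap is 0. Such a gap is never certain, and the instruction not to exclude is not at fault there.

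**The case against.** The best defence is that the two branches face different problems. With an unknown start date, the censoring date (previous stop + 57 days) is known and only the gap length is in doubt. With an unknown stop date, the censoring date itself is unknown, in the worked case over most of a year. Declining to impute so vague a date is understandable. This explains why the branches differ, and it means they are not a flat contradiction. It does not justify keeping all later data when the gap is certain, because latest possible stop + 57 days is an available bound. SAP Section 11.6.1 already takes the latest consistent date for a partial last stop date, within its limits on death and visit dates.

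It could also be said that the study team's review before database freeze would catch such cases. That review assesses whether deviations warrant exclusion; Section 11.1.2 gives it no stated power to override an explicit instruction not to exclude.

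Three stronger readings are tempting but not supported:

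- *Every year-only stop date is ignored.* No. A partial last stop date is imputed under Section 11.6.1 and does drive censoring.
- *Off-drug subjects are wrongly kept in a Per-Protocol population.* The SAP defines no such population; it censors data. An affected subject has a later recorded start, so the retained follow-up mixes the gap with time back on drug. It still ends at treatment stop date + 57 days, or earlier under another criterion.
- *The rule biases towards non-inferiority.* Off-drug dilution pulls the ratio towards 1. That helps non-inferiority only if the true ratio exceeds 1; below 1 it works against both non-inferiority and superiority.

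**Conclusion.** The point holds in limited form. Followed literally, the stop-date branch keeps data that criterion 05 says to censor whenever a non-last stop date is year-only and the next start is on or after 26 February of the following year. No other part of the SAP supplies the missing test.

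The weight is low. The rule feeds one sensitivity analysis; the primary ITT, On-treatment and On-therapy analyses do not use it. It needs an intermediate dosing entry with neither day nor month of stop, followed by a late enough restart. The SAP gives no count; few subjects are likely, and there may be none. Any effect on the Per-Protocol hazard ratio is dilution towards 1, of a size that cannot be computed from the SAP. This is a worthwhile tidy-up and does not threaten the trial's conclusion.

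**What to change.** Add a step to the stop-date branch of Section 11.1.2, ahead of the year-only line: *if the latest stop date compatible with that entry's start date and with the next start date still leaves 56 or more days off study treatment, exclude data from that latest stop date + 57 days onward.*

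State that this is the latest bound on the censoring date, since the true stop may be earlier. In the worked case, a true stop on 11 Feb 2016 would call for censoring from 8 Apr 2016, against 26 Feb 2017 under the new step, so up to 324 days could still be retained. Note also that the choice follows the latest-consistent-date convention of Section 11.6.1.

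The cost is one sentence and one extra condition in the derivation program. It needs no new data and can be settled before unblinding. A blinded count of affected dosing entries would show whether it changes anything.
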